5.1.2 Concomitant medication date imputation

5.1.2.1 Concomitant treatment end date imputation

1. If CM end day is missing and CM month/year are non-missing then impute CM day as the minimum of treatment end date and the last day of the month.
2. If CM end day/month are missing and CM year is non-missing then impute CM day as the minimum of treatment end date and the end of the year (31DECYYYY).
3. Only include if ongoing records will have an imputed CM end date. If CM day/month/year is missing then use the treatment end date + 1 day as the imputed CM end date.
4. If imputed CM end date is less than the CM start date, use the CM start date as the imputed CM end date.
5. If imputed CM end date is greater than date of death, date of cutoff, or the last visit date, then use the minimum of date of death, date of cutoff, and the last visit date as the imputed CM end date.

5.1.2.2 Concomitant treatment start date imputation

The following table explains the notation used in the logic matrix. Please note that **missing start dates** will not be imputed.

	Day	Month	Year
Partial CMD Start Date	Not used	MON	YYYY
Treatment Start Date	Not used	TRTM	TRTY

The following matrix explains the logic behind the imputation.

	MON MISSING	MON < TRTM	MON = TRTM	MON > TRTM
YYYY MISSING	(1) Uncertain	(1) Uncertain	(1) Uncertain	(1) Uncertain
YYYY < TRTY	(2.a) Before Treatment Start	(2.c) Before Treatment Start	(2.c) Before Treatment Start	(2.c) Before Treatment Start
YYYY = TRTY	(4.a) Uncertain	(4.b) Before Treatment Start	(4.a) Uncertain	(4.c) After Treatment Start

YYYY > TRTY	(3.a) After Treatment Start	(3.c) After Treatment Start	(3.c) After Treatment Start	(3.c) After Treatment Start
-------------	----------------------------------	----------------------------------	----------------------------------	----------------------------------

1. If the CM start date year value is missing, the imputed CM start date is set to one day prior to treatment start date.
2. If the CM start date year value is less than the treatment start date year value, the CM started before treatment. Therefore:
 - a. If the CM day and month are missing, the imputed CM start date is set to the mid-year point (01JulYYYY).
 - b. If CM month is missing but day is not missing, the observed start date will be used with month imputed as JulYYYY.
 - c. Else if the CM month is not missing, the imputed CM start date is set to the mid-month point (15MONYYYY).
3. If the CM start date year value is greater than the treatment start date year value, the CM started after treatment. Therefore:
 - a. If the CM day and month are missing, the imputed CM start date is set to the year start point (01JanYYYY).
 - b. If CM month is missing but day is not missing, the observed start date will be used with month imputed as JanYYYY.
 - c. Else if the CM month is not missing, the imputed CM start date is set to the month start point (01MONYYYY).
4. If the CM start date year value is equal to the treatment start date year value:
 - a. And the CM day and CM month are missing or the CM day is missing and CM month is equal to the treatment start date month, then the imputed CM start date is set to one day prior treatment start date.
 - b. Else if the CM month is less than the treatment start date month, the imputed CM start date is set to the mid-month point (15MONYYYY).
 - c. Else if the CM month is greater than the treatment start date month, the imputed CM start date is set to the month start point (01MONYYYY).

If complete (imputed) CM end date is available and the imputed CM start date is greater than the (imputed) CM end date, then imputed CM start date should be set to the (imputed) CM end date.

5.2 Statistical models

5.2.1 Primary analysis and supportive analyses

The multiple imputation for the primary analysis and the supportive analyses will be done using the Five Macros (Carpenter et al. 2013). The code of the Mixed Model with Repeated Measures

(MMRM) is included in macro 'part3_55' for the primary analysis and the supportive analyses. To get the 90% confidence intervals, the default of 'Alpha' as an input parameter of the macro 'part3_55' can be changed to 0.1:

```
%part3(Jobname=<XXX>
, anref=0
, alpha=0.1
, Label=<YYY>);
```

The model fitting part included in the macro is essentially equivalent to fitting the MMRM model to each individually imputed data set using the following SAS code:

Change from baseline in binocular DCNVA = intercept + treatment + baseline binocular DCNVA + visit + age group + treatment*visit + error.

The following SAS code can be used to perform these analyses:

```
PROC MIXED DATA=<Dataset> order=Internal;
  CLASS USUBJID <Treatment> <VISIT> <AGE GROUP>;
  MODEL <Chg_DCNVA> = <Treatment> <VISIT> <VISIT by Treatment>
        <Baseline binocular DCNVA> <Age group> /
DDFM=KENWARDROGER
        ALPHA=0.05;
  REPEATED <VISIT>/type=UN subject=USUBJID;
  LSMEANS <VISIT>*<Treatment> / DIFF CL ALPHA = 0.05;
  ODS OUTPUT LSMEANS=outLsm
             DIFFS=DiffS;
RUN;
```

The terms in the brackets are to be adjusted according to the real data set and variable names.

Names of the output data sets from the Five Macros are: &jobname._datafinal (final multiply imputed data sets) and &jobname._out (model fitting statistics of the multiply imputed data sets). The two-sided p-value provided by the ESTIMATE statement will be converted to one-sided p-value as follows:

- If the mean difference is ≥ 0 , the one-sided p-value = two-sided p-value/2;
- If the mean difference is < 0 , the one-sided p-value = 1 – two-sided p-value/2.

The summary statistics of the primary variable based on the multiply imputed data sets can be obtained using the following SAS macro:

```
%macro prim_sum(datain,Visit,Trt,Resp,Imput,dataout) ;
PROC SORT DATA=&datain;
BY &Visit &Imput &Trt;
RUN;

ODS OUTPUT ConfLimits=SUM;
PROC TTEST DATA = &datain;
BY &Visit &Imput;
CLASS &Trt;
```

```
VAR &Resp;  
RUN;
```

```
DATA SUM;  
SET SUM;  
BY &Visit &Imput;  
where method^="Satterthwaite";  
keep &Visit &Imput Class Mean StdDev;  
RUN;
```

```
PROC SORT data=SUM;  
BY &Visit Class &Imput;  
RUN;
```

```
PROC MIANALYZE data=SUM alpha=0.1; *for the 90% confidence intervals;  
BY &Visit Class;  
ODS OUTPUT PARAMETERESTIMATES=&dataout;  
MODELEFFECTS Mean;  
STDERR StdDev;  
RUN;  
%mend ;
```

To call the above macro, &datain should be &jobname._datafinal, &visit is the variable used to indicate different visits <Visit>, &trt is the variable indicating treatment arms <Treatment>, &Resp is the response variable <Chg_DCNVA>, &imput is the variable indicating sets of different imputed data. If only data at Month 3 needs to be presented, shown by stratum, the <Visit> variable can be supplied by stratification variable when calling the macro.

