5.2.2 Secondary analysis

The secondary analysis results can be performed by running the following SAS macro (Ratitch et al. 2013):

```
/*This macro performs all needed secondary analyses for UNR844A2203 study*/  
%macro secondary(datain,Trt,Visit,Imput,Strata,Resp,method,dataout_sum,dataout_cmh,dataout_p) ;  
  
PROC SORT data=&datain;  
BY &Visit &Trt &Imput;  
RUN;  
  
/*****Summary statistics of secondary endpoint at M3*****/  
/*****/  
/*Estimate proportions of responders in each arm*/
```

```
PROC FREQ DATA=&datain;  
TABLES Resp_MA / cl binomial(level=2);  
BY &Visit &Trt &Imput;  
ODS OUTPUT BINOMIAL=prop;  
RUN;  
run;
```

*** From ODS output dataset BINOMIAL, create a dataset containing estimated proportion of responders in each treatment arm and their standard errors;

```
DATA prop_trt;  
MERGE  
prop(WHERE=(Label1="Proportion"))  
KEEP=&Imput &Visit &Trt nValue1 Label1  
RENAME=(nValue1=prop)  
prop(WHERE=(Label1="ASE"))  
KEEP=&Imput &Visit &Trt nValue1 Label1  
RENAME=(nValue1=prop_se);  
BY &Visit &Trt &Imput;  
RUN;
```

```
*** Combine proportion estimates;  
PROC SORT DATA=prop_trt; BY &Visit &Trt &Imput; RUN;  
PROC MIANALYZE DATA=prop_trt alpha=0.1;  
MODELEFFECTS prop;  
STDERR prop_se;  
BY &Visit &Trt;  
ODS OUTPUT PARAMETERESTIMATES=&dataout_sum;  
RUN;
```

```
/*****  

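### SAP macro prim_sum passes the standard deviation to PROC MIANALYZE as the standard error, so its 90% limits for arm means are about sqrt(n) too wide; the primary MMRM result is unaffected

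*SAP*

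**What the plan says.** SAP section 5.2.1 introduces the macro in this way: "The summary statistics of the primary variable based on the multiply imputed data sets can be obtained using the following SAS macro". The macro runs PROC TTEST by visit and imputation, sends the ConfLimits table to a data set, removes the Satterthwaite row and reduces the rest with "keep &Visit &Imput Class Mean StdDev". The pooling step opens with "PROC MIANALYZE data=SUM alpha=0.1; *for the 90% confidence intervals", names the mean as the effect to be pooled, and supplies its standard error through "STDERR StdDev".

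The text after the macro explains how to call it, including a use by stratum: "If only data at Month 3 needs to be presented, shown by stratum".

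Two neighbouring pieces of the SAP matter for comparison:

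- The MMRM macro in the same section has its own setting for interval width ("To get the 90% confidence intervals, the default of" the alpha parameter is changed to 0.1) and writes to its own output data set.
- The macro for the secondary endpoint, in section 5.2.2, takes the asymptotic standard error of the proportion from PROC FREQ and pools it with "STDERR prop_se".

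**The concern.** PROC MIANALYZE treats whatever it is given in the STDERR statement as the standard error of the estimate being pooled. For an arm mean that is SD/sqrt(n). The macro gives it the SD. Neither n nor a standard error survives the KEEP list, so no later line could make the correction.

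If the resulting limits are tabulated, the 90% intervals around the arm means, by visit or by stratum, will greatly overstate the uncertainty. The standard-error column will in fact be close to an SD, and the t-statistics and p-values in the same output will be wrong. The pooled-difference row also passes the filter and receives an SD. If it were printed, its interval would appear to contradict the MMRM result for the same comparison.

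The section 5.2.2 macro fills the same position correctly, which suggests a coding slip and not a deliberate choice.

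**Working it through.** **Inputs.** From SAP 3.1.1: difference 4.9 letters, common SD 6.02, 33 completers per arm aged 45 to 55, 72 enrolled (36 per arm at 1:1), one-sided 5%. From the macro: 90% two-sided limits, so z = 1.645.

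**Check of the plan's own figure.** The SAP states no interval width for this macro, so the only figure to reproduce is the power. The standardised difference is 4.9 / (6.02 × sqrt(2/33)) = 3.306. The normal approximation gives Φ(3.306 − 1.645) = 95.2%, and the noncentral t with 64 df gives 94.8%. Both agree with the stated approximate 94%, so the SD and n are used as the plan intends.

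**Formula.** Rubin's total variance is T = W + (1 + 1/m)B, where W is the within-imputation and B the between-imputation variance. As coded, W = SD². The correct value is W = SD²/n for an arm mean and W = SD²(1/n₁ + 1/n₂) for the pooled difference. When B is small, the width ratio is sqrt(n) for an arm mean and sqrt(n/2) for the difference.

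**Arm means, B small.** The coded half-width is 1.645 × 6.02 = 9.90 letters whatever n is.

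| Subjects per arm | Correct half-width (z) | Ratio (z) | Correct half-width (t) | Ratio (t) |
|---|---|---|---|---|
| 33 | 1.645 × 6.02/√33 = 1.72 | 5.74 | 1.78 | 5.58 |
| 36 | 1.645 × 6.02/√36 = 1.65 | 6.00 | 1.70 | 5.84 |
| 16 to 18 (assumed, one two-level factor) | 2.48 to 2.33 | 4.0 to 4.24 | 2.64 to 2.47 | 3.75 to 4.0 |
| 8 to 9 (assumed, four crossed strata) | 3.50 to 3.30 | 2.8 to 3.00 | 4.03 to 3.73 | 2.46 to 2.7 |

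The stratum rows assume an even spread over strata, which the documents do not give.

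**Difference row, only if tabulated.** At 4.9 letters with 33 per arm, the coded interval is 4.9 ± 9.90, that is −5.0 to 14.8. The correct one is 4.9 ± t(0.95, 64) × 6.02 × sqrt(2/33) = 4.9 ± 2.47, that is 2.4 to 7.4. The ratio is 9.90/2.47 = 4.0.

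**Effect of between-imputation variance.** B enters both versions and lowers the ratio a little. At 36 per arm the arm-mean ratio is 5.85, 5.70, 5.39 and 5.05 for an assumed fraction of missing information of 5%, 10%, 20% and 30%.

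**Simulation.** Two simulations imputed under MAR without covariates, with 36 per arm and 100 imputations (both the model and the counts are assumptions).

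- With 4 of 36 imputed (400 repeats), the mean half-width was 9.85 as coded and 1.74 when corrected, a ratio of 5.65.
- With 3 of 36 imputed (4,000 repeats), the ratio was 5.73. Coverage of the nominal 90% interval was 100% as coded and 88.9% when corrected. For the difference row the ratio was 4.06, with coverage of 100% and 89.9%.

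**The case against.** The strongest reply is that the plan never asks for these intervals. SAP section 2.1 lists the number of observations, mean, SD, median and range for continuous variables, and confidence intervals only for treatment differences. The difference interval comes from the MMRM. The macro is offered as something that can be used for summary statistics, and the only link to intervals is one code comment. Perhaps the SD was passed so that it could be displayed. The error also widens intervals, so it cannot produce a false claim of benefit, and a half-width of 9.9 letters with an SD of 6.02 would look implausible to a careful reader.

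Much of this stands. The effect is conditional on the output being reported, and no decision rests on it. The difference row is the least likely to be shown. The crossed-strata figure is illustrative, because the four-level variable is defined for the secondary macro while section 5.2.1 refers only to a stratification variable. The t-based half-widths are not quite what a corrected STDERR input returns: unless complete-data degrees of freedom are also supplied, the limits with little missing data stay close to the z values. The contents of the ConfLimits table, including the surviving pooled-difference row, are standard SAS behaviour and are not stated in the SAP.

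The display reading does not rescue the code. Setting alpha to 0.1 serves a purpose only if limits are read from the output. What MIANALYZE returns is sqrt(mean SD² + (1 + 1/m)B) under a standard-error label. That is neither the average SD nor the standard error of the mean.

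**Conclusion.** The concern holds. As written, the macro supplies the wrong quantity as the standard error. For the primary age group, its 90% limits for an arm mean are about 5.6 to 6.0 times too wide when little information is missing, and about 5 times at 36 per arm if 30% is missing. By stratum the factor is roughly 2.5 to 4, depending on assumed cell sizes; for the difference row it is about 4.

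This is an error in descriptive output only. It should be corrected before the code is used, because this is the only method the visible SAP gives for summarising the primary variable across imputations. It gives no reason to doubt the primary or secondary inference.

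**What to change.** Take the standard error from the PROC TTEST Statistics table. Alternatively, bring n into the data set and derive SD/sqrt(n) for each arm row and SD × sqrt(1/n₁ + 1/n₂) for the pooled-difference row. Add that variable to the KEEP list and name it in the STDERR statement.

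If the difference is to be reported only from the MMRM, drop the pooled-difference row in the same filter. If an SD is wanted in the table, average it across imputations in a separate step and label it as an SD.

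The cost is a few lines of SAP code and the matching program. No new data are needed, and the primary analysis does not change.

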5.2.2 Secondary analysis

The secondary analysis results can be performed by running the following SAS macro (Ratitch et al. 2013):

```
/*This macro performs all needed secondary analyses for UNR844A2203 study*/  
%macro secondary(datain,Trt,Visit,Imput,Strata,Resp,method,dataout_sum,dataout_cmh,dataout_p) ;  
  
PROC SORT data=&datain;  
BY &Visit &Trt &Imput;  
RUN;  
  
/*****Summary statistics of secondary endpoint at M3*****/  
/*****/  
/*Estimate proportions of responders in each arm*/
```

```
PROC FREQ DATA=&datain;  
TABLES Resp_MA / cl binomial(level=2);  
BY &Visit &Trt &Imput;  
ODS OUTPUT BINOMIAL=prop;  
RUN;  
run;
```

*** From ODS output dataset BINOMIAL, create a dataset containing estimated proportion of responders in each treatment arm and their standard errors;

```
DATA prop_trt;  
MERGE  
prop(WHERE=(Label1="Proportion"))  
KEEP=&Imput &Visit &Trt nValue1 Label1  
RENAME=(nValue1=prop)  
prop(WHERE=(Label1="ASE"))  
KEEP=&Imput &Visit &Trt nValue1 Label1  
RENAME=(nValue1=prop_se);  
BY &Visit &Trt &Imput;  
RUN;
```

```
*** Combine proportion estimates;  
PROC SORT DATA=prop_trt; BY &Visit &Trt &Imput; RUN;  
PROC MIANALYZE DATA=prop_trt alpha=0.1;  
MODELEFFECTS prop;  
STDERR prop_se;  
BY &Visit &Trt;  
ODS OUTPUT PARAMETERESTIMATES=&dataout_sum;  
RUN;
```

```
/*****  

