### **12.8.2 Secondary endpoint(s)**

Assuming the proportion of subjects achieving 75 or more ETDRS letters in binocular DCNVA at Month 3 are 40.5% and 10.5% for UNR844-CI and placebo, respectively, based on the results of the prior study in presbyopic subjects, 66 subjects (33 in each arm) aged 45 to 55 years are required to be completed to achieve an approximate power of 82% at 5% (one-sided) significance level.

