1.1 Study design

Figure 1-1 Study Design

This is a multi-center, double-masked, placebo-controlled, randomized, parallel-group study. The total duration of the study will be approximately 3 months ([Figure 1-1](#)). Approximately 120 presbyopic subjects will be enrolled into the study.

Screening and Baseline: Subjects will be screened for eligibility followed by a baseline visit after which they will be randomized to receive either lipoic acid choline ester chloride (UNR844-Cl) or placebo, dosed one drop in each eye twice-daily for 3 months.

Randomization will be stratified based on binocular distance-corrected near visual acuity (DCNVA) (59 Early Treatment Diabetic Retinopathy Study [ETDRS] letters or less; 60 ETDRS letters or more) and age (45 to 50 years, 51 to 55 years and 56 to 65 years) at baseline.

Subjects will be randomized 1:1 within each stratum to either UNR844-Cl or placebo.

Randomized subjects will attend the following study visits after baseline: at Week 2, Month 1, Month 2 and Month 3.

[figure not shown]
The primary objective of this study is to evaluate the efficacy of topical UNR844-Cl ophthalmic solution in presbyopic subjects aged 45 to 55 years by assessing the change in binocular DCNVA from baseline when compared to placebo after three months of treatment.

[figure not shown]
There is no interim analysis planned.

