3.1.1 Primary endpoint

Assuming a mean difference of 4.9 ETDRS letters with a common standard deviation of 6.02 ETDRS letters in change from baseline in binocular DCNVA at 3 months between UNR844 and placebo, based on the results of the prior study in presbyopic subjects, 66 subjects (33 in each arm) aged 45 to 55 years are required to complete the study to achieve an approximate power of 94% at 5% (one-sided) significance level. Assuming about 90% subjects will complete the study, a total of 72 subjects for the primary efficacy endpoint will be enrolled.

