3.1.2 Secondary endpoints

Assuming the proportion of subjects achieving 75 or more ETDRS letters in binocular DCNVA at Month 3 are 40.5% and 10.5% for UNR844-CI and placebo, respectively, based on the results of the prior study in presbyopic subjects, 66 subjects (33 in each arm) aged 45 to 55 years are required to be completed to achieve an approximate power of 82% at 5% (one-sided) significance level.

4 Change to protocol specified analyses

Not applicable.

5 Appendix

Statistical methods are described in the main part of the clinical study report. This appendix provides further details on the statistical derivation and practical implementation.

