*****Perform CMH test*****  
*****/
```

*** Step I: Obtain Mantel-Haenszel estimate of the common odds ratio adjusted for &Strata ***.

```
PROC SORT DATA=&datain;  
by &Visit &Imput;  
RUN;
```

```
PROC FREQ DATA=&datain;  
TABLES &Strata*&Trt*&Resp / CMH;  
ODS OUTPUT COMMONRELRISKS=comrrout;  
BY &Visit &Imput;  
RUN;
```

```
*** Log-transform odds ratio estimates  
and obtain standard error from confidence intervals ***;  
DATA ormh_t; SET comrrout(WHERE=(StudyType="Case-Control"));  
log_or_mh_value=log(VALUE);  
log_or_mh_se=(log(UPPERCL)-log(LOWERCL))/(2*quantile('Normal',.975));  
RUN;
```

```
*** Combine proportion estimates;  
PROC SORT DATA=ormh_t; BY &Visit &Imput; RUN;
```

```
PROC MIANALYZE DATA=ormh_t alpha=0.1;
MODELEFFECTS log_or_mh_value;
STDERR log_or_mh_se;
BY &Visit;
ODS OUTPUT PARAMETERESTIMATES=log_cmh;
RUN;
```

```
data &dataout_cmh ;
set log_cmh ;
Common_or = exp(Estimate);
*Or_upper = exp(Estimate+quantile('Normal',.95)*StdErr);
*Or_lower = exp(Estimate-quantile('Normal',.95)*StdErr);
e_lcl = exp(LCLMean);
e_ucl = exp(UCLmean);
Keep &Visit Common_or e_lcl e_ucl;
run;
```

```
PROC FREQ DATA=&datain;
TABLES &Strata*&Trt*&Resp / CMH;
ODS OUTPUT CMH=cmh;
BY &Visit &Imput;
RUN;
```

```
%if &method=1 %then %do;
/*****Step II/Option 1: To obtain p-values, perform CMH test
by applying Wilson-Hilferty transformation to the CMH statistic*****/
*** Apply Wilson-Hilferty transformation to the CMH statistic and
standardize the resulting normal variable;
DATA cmh_wh; SET cmh(WHERE=(AltHypothesis="General Association"));
cmh_value_wh=((VALUE/DF)**(1/3) - (1-2/(9*DF)))/SQRT(2/(9*DF));
cmh_sterr_wh = 1.0;
RUN;
*** Combine results;
PROC MIANALYZE DATA=cmh_wh;
by &Visit;
ODS OUTPUT PARAMETERESTIMATES=mian_cmh_wh;
MODELEFFECTS cmh_value_wh;
STDERR cmh_sterr_wh;
RUN;
*** Compute one-sided p-value;
DATA &dataout_p; SET mian_cmh_wh;
IF tValue > 0 THEN Probt_WH = Probt/2;
ELSE Probt_WH = 1-Probt/2;
KEEP &Visit Probt_WH;
RUN;
%end;
```

```
%if &method=2 %then %do;
/*****Step II/Option 2: To obtain p-values, perform CMH test
by applying Rubin & Li et al's transformation to the CMH statistic*****/
DATA cmh_rub; SET cmh(WHERE=(AltHypothesis="General Association"));
KEEP &Visit &Imput DF Value;
RUN;
```

```
PROC SORT DATA=cmh_rub ;
```

```
BY &Visit &Imput;
RUN;
```

[figure not shown]
```
*** Implement pooling procedure described in equations (3) and (4);
```

[figure not shown]
```
PROC IML;
USE cmh_rub ;
READ ALL VAR {Value} INTO chval;

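### The placebo responder-rate 90% interval in SAP 5.2.2 is built symmetrically on the raw scale from Wald standard errors; at the planned 10.5% rate it falls short of its level, mostly by lying too low, and often has a negative lower limit

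*SAP*

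**What the plan says.** The secondary macro in SAP 5.2.2 estimates the responder proportion by arm in every imputed data set and carries forward that estimate with its asymptotic (Wald) standard error. It then pools the two with "PROC MIANALYZE DATA=prop_trt alpha=0.1". The effect being pooled is the proportion itself, with no transformation, so the result is a symmetric 90% interval around the pooled proportion. The closing paragraph of 5.2.2 describes this output as the summary statistics for the binary variable. No truncation at zero, alternative interval or rule for an arm without responders is given.

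The same macro pools the Mantel-Haenszel odds ratio after a log transformation ("log_or_mh_value=log(VALUE") and exponentiates the limits.

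The planning rates in SAP 3.1.2 "are 40.5% and 10.5% for UNR844-CI and placebo, respectively"; Protocol 12.8.2 has the same figures. SAP 3.1.2 states that "66 subjects (33 in each arm) aged 45 to 55 years are required to be completed".

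**The concern.** A Wald interval for a proportion behaves poorly when the sample is small and the rate is near zero. The planned placebo arm has both features: at 10.5% of 33 subjects, about 3.5 responders are expected. At the expected count the lower limit stays just above zero, so the problem is easy to overlook. It appears at the lower counts that this rate often produces.

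At stake is the interval printed beside the placebo rate for the only secondary efficacy endpoint. A negative limit or a zero-width interval would have to be dealt with after unmasking. An interval that tends to sit too low also understates how high the placebo rate could be, which flatters the informal comparison with the active arm.

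**Working it through.** **Inputs**
- Responder rates 40.5% (active) and 10.5% (placebo): SAP 3.1.2 and Protocol 12.8.2.
- 33 completers per arm: SAP 3.1.2.
- 36 per arm: SAP 3.1.1 enrols 72 subjects aged 45 to 55 ("Assuming about 90% subjects will complete the study, a total of 72 subjects for the primary efficacy endpoint will be enrolled"), and allocation is 1:1 (SAP 1.1), so 72/2 = 36. Missing Month 3 values are imputed (SAP 2.7.3), so the analysed number is nearer 36 than 33.
- Interval level 90%, z = 1.645: SAP 5.2.2.

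**Step 1. Reproduce the plan's own figure.** SAP 3.1.2 says the sample will "achieve an approximate power of 82% at 5% (one-sided) significance level". With a continuity correction:
- Null standard error: sqrt(2 × 0.255 × 0.745/33) = 0.1073, where 0.255 is the mean of the two rates.
- Alternative standard error: sqrt((0.405 × 0.595 + 0.105 × 0.895)/33) = 0.1007.
- Power = Φ[(0.300 − 1/33 − 1.645 × 0.1073)/0.1007] = Φ(0.925), about 82%.

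The stated power is reproduced, so the inputs are read correctly.

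**Step 2. The coded interval, placebo, n = 33, no imputation.** The limits are p ± 1.645 × sqrt(p(1 − p)/33), with p = x/33. Probabilities are binomial (33, 0.105).

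| Responders x | Probability | 90% limits |
|---|---|---|
| 0 | 0.0257 | 0.0% to 0.0% |
| 1 | 0.0995 | −1.9% to 7.9% |
| 2 | 0.1869 | −0.8% to 12.9% |
| 3 | 0.2265 | 0.9% to 17.3% |
| 4 | 0.1993 | 2.8% to 21.5% |
| 5 | 0.1356 | 4.9% to 25.4% |
| 6 | 0.0743 | 7.1% to 29.2% |
| 7 | 0.0336 | 9.5% to 32.9% |
| 8 | 0.0128 | 12.0% to 36.5% |

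- The interval contains 10.5% only for x = 2 to 7. Coverage = 0.1869 + 0.2265 + 0.1993 + 0.1356 + 0.0743 + 0.0336 = 85.6%.
- Wholly below the true rate (x = 0 or 1): 12.5%. Wholly above (x of 8 or more): 1.9%. An equal-tailed 90% interval would have about 5% on each side.
- Negative lower limit (x = 1 or 2): 0.0995 + 0.1869 = 28.6%.
- Zero-width interval (x = 0): 2.6%.

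**Step 3. Placebo, n = 36, no imputation.** The same enumeration gives coverage of 87.3%, misses of 9.6% below and 3.1% above, and a negative limit in 23.8% of trials.

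**Step 4. Placebo, n = 36 with about 10% imputed.** The documents give neither the missing-data pattern nor the correlation with earlier visits. Simulations assumed correlations of 0.5 to 0.8, normal-model imputation and pooling by Rubin's rules. Coverage was about 85% to 88%, with negative limits in about 30% to 32% of trials. Imputation does not remove the problem.

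**Step 5. Sensitivity to arm size.** Coverage moves in steps because counts are discrete. Placebo coverage is 80.5% at n = 30, 84.8% at 32, 86.3% at 34, 87.3% at 36 and 90.4% at 38.

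**Step 6. Active arm, 40.5%.** Wald coverage is 88.1% at n = 33, where Wilson gives 92.5%. The two are equal at n = 32 (89.7%) and n = 34 (88.4%), and Wald is higher at n = 35 (91.5% against 88.0%). There are effectively no negative limits.

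**Step 7. Alternative for placebo.** Logit-scale or Wilson limits cover 92.2% at n = 33 and 90.4% at n = 36. When built from the pooled variance in the imputed case they cover about 93% to 94%. Example, 2 of 33: p = 0.0606, standard error 0.0415, logit −2.741, logit standard error 0.0415/(0.0606 × 0.9394) = 0.730. The limits −2.741 ± 1.645 × 0.730 back-transform to 1.9% and 17.6%, against −0.8% and 12.9% as coded.

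**The case against.** The strongest reply is materiality. The secondary hypothesis is tested by the stratified CMH test, and its p-value and the odds-ratio interval come from separate steps of the macro. That stands: neither is affected. SAP 2.1 also promises confidence intervals for treatment differences, not per arm, so the plan does not say outright that these limits will be tabulated. This stands in part, since the macro is written to produce them at 90% and the output is labelled as the endpoint's summary statistics.

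A reader might infer three stronger claims that the documents do not support:
- **That the intervals are too narrow in general.** At n = 33 the mean Wald width is 27.7 points in the active arm against 26.7 for Wilson, so Wald is wider there. For placebo it is 16.7 against 17.3. The placebo fault is mainly one of location.
- **That the active arm is also affected.** The gap at n = 33 comes from discreteness and disappears or reverses at neighbouring sizes.
- **That log-scale pooling of the odds ratio shows an error for the proportion.** Ratios are conventionally pooled on the log scale. The contrast shows only that a transformation is already in use in this macro.

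It is also fair to say that 85.6% is one point on a sawtooth and that 36 per arm is closer to the planned analysis. The shortfall there is still about 3 points, with the same lopsidedness.

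**Conclusion.** The point holds for the placebo interval only. At the planned 10.5% rate the coded 90% interval covers 85.6% at n = 33, 87.3% at n = 36, and about 85% to 88% with 36 per arm and about 10% imputed. The misses fall mostly on the low side, and the lower limit is negative in roughly 24% to 32% of trials. The exact figures rest on the plan's placebo rate and stated arm sizes. The imputed case rests on an assumed missing-data pattern and correlation. If the true placebo rate is well above 10.5%, the problem shrinks. It is a minor descriptive defect with no bearing on the secondary test, but it is better settled before unmasking.

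**What to change.** Keep the pooling step as it is, and take from it the pooled proportion p and the total variance T. In a following data step:
- Set SE_logit = sqrt(T)/(p(1 − p)).
- Form logit(p) ± t × SE_logit, where t is the 95th percentile of the t distribution with the pooled degrees of freedom (the normal quantile if there is no between-imputation variance), and back-transform.
- If p is 0 or 1, use a 90% Wilson interval with the arm size. For 0 of 33 this gives 0% to 7.6%.

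Transforming after pooling matters. Taking the logit within each imputed data set fails whenever a single imputation has no responders, even if others have some.

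The cost is a few lines of SAS and a sentence in SAP 2.7.2. Placebo limits move upward and are slightly conservative at the planned sizes. Coverage will still vary with arm size (87.6% at n = 30 to 92.6% at n = 32 without imputation), but no limit can fall below zero. If per-arm limits are not meant to be reported, saying so in the SAP would also settle the point.
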